12.1.2 Unexpected Adverse Reaction

An adverse reaction, the nature or severity of which is not consistent with the applicable product information (e.g., IB for an unauthorised IP or summary of product characteristics for an authorised product).

Comment: When the outcome of the adverse reaction is not consistent with the applicable product information this adverse reaction should be considered as unexpected.

12.1.3 Serious Adverse Event

Any untoward medicinal occurrence or effect that at any dose:

- Results in death
- Is life-threatening
- Requires hospitalisation or prolongation of existing hospitalisation
- Results in persistent or significant disability or incapacity
- Is a congenital anomaly or birth defect

Comments: Life-threatening in the definition of an SAE or serious adverse reaction refers to an event in which the subject was at risk of death at the time of event; it does not refer to an event which hypothetically might have caused death if it was more severe.

Medical judgement should be exercised in deciding whether an AE/reaction is serious in other situations. Important AEs/reactions that are not immediately life-threatening or do not result in death or hospitalisation but may jeopardise the subject or may require intervention to prevent one of the other outcomes listed in the definition above, should also be considered serious.

12.2 Reporting of Adverse Events

All trial subjects will be carefully monitored for the occurrence of AEs during the trial period, from start of intake of the first dose of contrast agent until the follow-up visit. Also, telephone interviews will be made 2 days after MRE assessment to investigate if any AEs occurred during the first days after the examination. Any pregnancies occurring in the same trial period will be reported and followed.

Reported AEs will be followed up (see [Section 12.5](#) below). The Investigator will collect AEs with a non-leading question such as “have you experienced any new health problems or worsening of existing conditions” as well as reporting events directly observed or spontaneously volunteered by subjects.

Clearly related signs, symptoms and abnormal diagnostic procedure results should be grouped together and reported as a single diagnosis or syndrome whenever possible.

All AEs including but not limited to events reported by the subject, or reported in answer to an open question by the Investigator or member of this team, which fall into any of the above definitions must be recorded as an AE in the CRF and should include the following information:

- Brief description of the event (diagnosis)
- Start date (and time, if relevant)
- Stop date (and time, if relevant)
- Severity
- Action taken regarding trial treatment
- Opinion on causality
- Seriousness
- Outcome

AEs will be coded with Medical Dictionary for Regulatory Activities (MedDRA), the version of which will be provided in the trial report.

12.2.1 Severity

Severity describes the intensity of an event, and will be assessed as:

Mild: The AE does not interfere in a significant manner with the subject's normal functioning level. It may be an annoyance.

Moderate: The AE produces some impairment of function but not hazardous to health. It is uncomfortable and/or an embarrassment.

Severe: The AE produces significant impairment of functioning or incapacitation and/or it is a hazard to the subject.

If an AE changes in severity, the worst severity should be reported.

12.2.2 Causality

Causality will be assessed as:

Probable: A clinical event, including laboratory test abnormality, with a reasonable time sequence to administration of the drug, unlikely to be attributed to concurrent disease or other drugs or chemicals, and which follows a clinically reasonable response on withdrawal (dechallenge). Rechallenge information is not required to fulfil this definition.

Possible: A clinical event, including laboratory test abnormality, with a reasonable time sequence to administration of the drug, but which could also be explained by concurrent disease or other drugs or chemicals. Information on drug withdrawal may be lacking or unclear.

Unlikely: A clinical event, including laboratory test abnormality, with a temporal relationship to drug administration which makes a causal relationship improbable, and in which other drugs, chemicals or underlying disease provide plausible explanations.

12.3 Follow-up of Subjects after Adverse Events

AEs that are serious or those that the investigator assesses as relevant to follow from a trial perspective will be followed until they are recovered, stabilised, or recovered with sequelae. The date and outcome will be recorded on the AE form in the CRF. Other ongoing AEs will not be followed within the trial after the date of the follow-up visit.

12.4 Abnormal Laboratory Values

Other than electrolytes, safety laboratory parameters will not be assessed in this trial.

12.5 Reporting of Serious Adverse Events

The Investigator is responsible for ensuring that all SAEs are reported to the Sponsor immediately, by e-mail (preferred) or fax, but in any event **no later than** 24 hours of any site staff becoming aware of the event. All AEs that meet the criteria for SAE require the completion of a study specific SAE Form (or Additional Safety Information (ASI) Form).

This applies to all SAEs, whether they were considered to be related to the study treatment or not.

The following information is **mandatory** for the initial report:

- Subject trial identification data (ID)
- Trial treatment
- Start date (time, if relevant) of the trial treatment
- Brief description of the event (diagnosis)
- Start date (time, if relevant) of the event
- Seriousness criteria
- Causality assessment

The Investigator must report all SAEs to Sponsor immediately, i.e., within 24 hours (via email or fax) of learning of its occurrence. For this reporting, an SAE Form (provided in the Investigator File) needs to be completed. Follow-up information about a previously reported SAE must also be reported to Sponsor within 24 hours of receiving the information. This follow-up data must be provided on an ASI Form.

If a SAE occurred after signing informed consent, but before study treatment and the subject continues on study, a SAE must also be entered on the relevant Medical History page of the CRF.

The SAE report should provide a detailed description of the AE and should include anonymised copies of hospital records and other relevant documents.

All SAEs will need to be followed actively until resolution or stabilisation. The above is also applicable to follow-up SAE information.

The Sponsor is responsible for informing the Competent Authorities, the European Medicines Agency (EMA) and Ethics Committees of any individual case reports of SAEs that are determined to be reportable by the sponsor (i.e., adverse events considered as serious unexpected suspected adverse reactions [SUSARs]). SUSARs will be distributed by the Sponsor's pharmacovigilance team within 7-15 working days to the EMA (EudraVigilance) and concerned Competent Authorities and Ethics Committees, according to local regulations. The investigator will be notified of safety issues / SUSARs according to current legislation.

The sponsor is required by law to report to the health authorities in a written safety report: 1) all fatal or life-threatening SUSARs within seven (7) calendar days of initial notification; and 2) all other SUSARs within fifteen (15) calendar days of initial notification.

12.6 Precautions/Overdose

Risks associated with intake of oral contrast agents include dysphagia with aspiration and secondary pneumonia. Although patients with acute problems are excluded, a pre-emergency small bowel status might be aggravated to an established ileus by ingesting a large volume. Oral contrast agents should not be given to subconscious patients, to those with swallowing disorders, or an acute abdomen.

Known sensitivity or allergy to contrast agent ingredients are exclusion criteria in clinical studies. However, unknown sensitivities or allergies might cause reactions that may need to be medically treated.

Intravenously administered Gd may cause allergic reaction of various severity from a mild rush to intensive care unit treatment. This is especially true for those with allergic reactions to a contrast agent earlier in life. Allergic reaction may be triggered in those with asthmatic bronchitis and treated with beta-blockers. Routines for handling these cases are well known to the staff which is regularly trained in dealing with emergency cases. Equipment for emergency care treatment is available at the clinic and the clinic is located in close proximity to the hospital emergency care department. Neither iodine nor Gd should be administered to patients with severe kidney failure.

13 STATISTICAL METHODS

13.1 General statistical considerations

No statistical tests will be conducted. Confidence intervals may be constructed and will then be 2-sided and of 95% confidence.

Continuous data will be summarised using descriptive statistics (N, mean, median, standard deviation, minimum and maximum). Categorical data will be summarised by frequency tables (numbers and percentages).

Unless otherwise stated, all analyses will be done on observed cases without any substitution of missing values.

13.2 Sample Size

A total of 10 fully evaluable healthy volunteers will be included in the trial. The number of subjects is considered to be enough to draw clinical conclusions and is not based on any mathematical grounds.

13.3 Analyses Sets

All subjects who have fulfilled the trial will be included in the statistical evaluation.

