Statistical analyses	
All subjects who have completed the trial will be included in the statistical evaluation.
 
No statistical tests will be conducted. Confidence intervals may be constructed and will then be 2-sided and of 95% confidence.
 
Continuous data will be summarised using descriptive statistics (N, mean, median, standard deviation, minimum and maximum). Categorical data will be summarised by frequency tables (numbers and percentages).
 
Unless otherwise stated, all analyses will be done on observed cases without any substitution of missing values.

Schedule of Assessments

Visit/Contact	1	2	3	4	5
	Pre-screening	Screening	MRE examination	Blood sampling	F-U ⁽¹⁾ and early termination
Day	-21 to -1	0	14	15	Visit 2 +2 days
Visit window (days)			+/- 7 days	-	+ 2
Subject information	X	X			
In/exclusion criteria	(X) ⁽²⁾	X			
Informed consent		X			
Physical examination		X			
Pregnancy test ⁽³⁾		X			
Creatinine blood sample		X			
Subject demographics (incl. height and weight)		X			
Concomitant treatment	X	X	X	X	X
Concomitant illnesses	X	X			
Medical history	X	X			
Adverse event(s) recording			X ⁽⁴⁾	X	X
Placement of IV antecubital cannula			X ⁽⁵⁾		

Visit/Contact	1	2	3	4	5
	Pre-screening	Screening	MRE examination	Blood sampling	F-U ⁽¹⁾ and early termination
Day	-21 to -1	0	14	15	Visit 2 +2 days
Visit window (days)			+/- 7 days	-	+ 2
MRE Scan			X		
Dispensing of Lumentin® 44			X		
Administration of Gd contrast (6)			X		
Administration of Buscopan® (6)			X		
Evaluation of extension and distension of bowel filling agents			X		
Blood sampling			X ⁽⁵⁾ (pre-, 1, 2, 4, 6, 8h)	X (24h)	
Compliance			X		

- 1) Subjects will be contacted by telephone two to four working days post MRE assessment.
- 2) Only some of the criteria will be checked including, inclusion criterion 1 and exclusion criteria 2, 3, 4, 5, 6, 7, 8, 12 and 13.
- 3) Urine pregnancy test of all females who are not surgically sterile (hysterectomy or tubal ligation) or postmenopausal (i.e., experienced 12 consecutive months without menstruation).
- 4) Telephone interviews will be conducted 2 days after MRE assessment to investigate if any AEs occurred during the first days after the imaging procedure
- 5) An IV antecubital cannula will be placed for pre-blood samples and used during the first 8h including administration of gadolinium during the MRE procedure. Thereafter it will be discarded. Blood sampling on the following day (24h time point) will be drawn without a cannula.

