8.3 Subject Withdrawal and Replacement

8.3.1 *Withdrawal from Trial Therapy*

Subjects must be withdrawn if the intake of the contrast agent has to be stopped, please see section 9.2 Dosage and Administration.

8.3.2 *Withdrawal from Study*

Subjects may withdraw from the trial at any time and for any reason without prejudice to his or her future medical care.

Subjects must be withdrawn under the following circumstances:

- The subject withdraws consent
- Subjects who have not fasted (clear water allowed) for at least six hours prior to the intake of the contrast agent
- The subject is unable to drink at least 1.1 L of Lumentin® 44
- The subject is unable to complete the MRE examination, due to e.g., claustrophobia.
- Violation of eligibility criteria

Subjects withdrawn due to the above circumstances will be replaced by one of the five remaining eligible HV subjects on standby after screening.

Subjects may be required to withdraw after discussion with the Sponsor and/or Investigator for the following reasons:

- AEs
- Use of prohibited medication (see Section 10)
- At the discretion of the Investigator

In all cases, the reason(s) for withdrawal must be recorded on the Case Report Form (CRF). If a subject is prematurely withdrawn from the trial for any reason, the Investigator must make every effort to perform the evaluations described for the Early Termination Visit (see Section **Fel! Hittar inte referenskälla.**).

If a subject has withdrawn informed consent and still agrees to attend the Early Termination Visit, this will be documented on the CRF.

For subjects who are withdrawn after they receive the trial drug, the Early Termination page will be completed in the CRF.

HVs withdrawn prior or during the MRE examination (i.e., no evaluable MRE scan has been generated) will be replaced by a new HV. HVs withdrawn after the completion of MRE examination and NOT fulfilling the mandatory criteria for withdrawal listed above will not be replaced.

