9.2 Dosage and Administration

The Investigational products will be taken orally by the subject during a period of 30 minutes - 1 hour.

A volume of 1.1 L to 1.5 L shall be consumed. A steady intake rate of the contrast agent is recommended to guarantee fullness of the gastrointestinal tract from stomach to terminal ileum of the small bowel.

The intake of the contrast agent will be stopped in case of an AE occurs or if the subject is unable to consume more than 1.1 L within 1 and ½ hour. The subject will be withdrawn in case the intake of the contrast agent has to be stopped.

The subject will be withdrawn from the trial if the maximum volume of the Investigational product taken by the subject is less than 1.1 L.

There is no risk of overdose.

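### No all-dosed safety set is defined: the only named population is subjects who finished the trial, so adverse events that stopped intake can drop out of the TEAE/TEADR tables

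*Combined protocol and SAP*

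**What the plan says.** **Population.** Section 13.3 reads "All subjects who have fulfilled the trial will be included in the statistical evaluation". The synopsis has "All subjects who have completed the trial will be included in the statistical evaluation". No other analysis set is defined. Section 13.4 says that the collected data will be summarised descriptively with confidence intervals, and names no population. Under section 13.5, a clean file meeting held after data entry decides whether any subject is left out of the analysis; no criteria are given.

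**Stopping and withdrawal.** Section 9.2 states: "The intake of the contrast agent will be stopped in case of an AE occurs". The same rule applies when the minimum volume is not reached. It continues: "The subject will be withdrawn in case the intake of the contrast agent has to be stopped". Section 8.3.2 lists among the mandatory reasons for withdrawal: "The subject is unable to drink at least 1.1 L of Lumentin® 44".

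**Replacement.** After the mandatory list, section 8.3.2 says: "Subjects withdrawn due to the above circumstances will be replaced by one of the five remaining eligible HV subjects on standby after screening". Adverse events are not on that list. They are covered by the last paragraph of the section: "HVs withdrawn prior or during the MRE examination (i.e., no evaluable MRE scan has been generated) will be replaced by a new HV".

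**Data capture.** Section 8.3.2 also says: "For subjects who are withdrawn after they receive the trial drug, the Early Termination page will be completed in the CRF". Section 12 has all adverse events recorded and followed, and section 9.5 has the containers weighed before and after drinking.

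**Objective and outcome.** Safety and tolerability of intake is a secondary objective (6.2). The matching outcome in 7.2.2 is any TEAE or TEADR.

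**The concern.** A safety summary should cover everyone exposed. Here an adverse event during drinking is itself a reason for leaving the set that is analysed, and the subject's place goes to someone else, who counts only if they get through the drink. The subjects who say most about tolerability of intake are the ones the stated population leaves out. For adverse-event stops the direction is systematic and favours the product.

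Subjects who fail on volume without an adverse event are a different case. Including them would add to the denominator only, so leaving them out does not lower the TEAE percentage. What is lost is the tolerability information: how many people could not drink the minimum amount.

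No tests are planned, so the descriptive table is the whole safety result. With about ten subjects, one omitted subject can decide whether a type of event appears in it at all.

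**Working it through.** The planned number, 10 fully evaluable volunteers (13.2), is stated to have no mathematical basis, so there is no figure of the plan's own to reproduce. The check has two parts.

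**1. Following a subject through the rules**

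| Step | Adverse event stops intake | Cannot drink 1.1 L, no adverse event |
|---|---|---|
| Exposed to Lumentin 44 | Yes | Yes |
| Withdrawn | Yes (9.2, 8.3.1) | Yes (9.2, 8.3.2) |
| Replaced | Yes (8.3.2, last paragraph) | Yes (8.3.2, mandatory list) |
| Data on the CRF | Yes (Early Termination page, AE form) | Yes (Early Termination page, container weights) |
| Completed the trial | No | No |
| In the population named in 13.3 | No | No |
| Brought back by 13.4 or 13.5 | Not required | Not required |

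**2. How large the effect could be**

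The documents give no rate of stopped intake, so the rate q is an assumption. The chance that at least one of the first 10 dosed subjects is stopped, and so omitted, is 1 − (1 − q)^10:

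- q = 5%: 1 − 0.95^10 = 1 − 0.599 = 40.1%
- q = 10%: 1 − 0.90^10 = 1 − 0.349 = 65.1%

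The protocol's background data do not narrow this much. Section 7.3.1 reports nausea in 2 + 3 = 5 subjects on Lumentin 44, and 7.3.2 gives 73 earlier subjects in all, so 5/73 = 6.8%. The timing of the nausea is not given. If none of it stopped intake the chance is 0%; if all of it did, it is 1 − (1 − 5/73)^10 = 50.8%. Those subjects were patients, not healthy volunteers. Average intake in the earlier trials was 1026 mL, below the new 1.1 L minimum, which makes volume failures plausible. But those subjects were asked for 0.75 to 1.5 L, and this trial recruits mainly young volunteers.

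Effect of one omitted adverse-event stop, with exact (Clopper-Pearson) two-sided 95% intervals:

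| Situation | Completers only | All dosed |
|---|---|---|
| Event seen only in the stopped subject | 0/10 = 0% (0 to 30.8) | 1/11 = 9.1% (0.2 to 41.3) |
| Any TEAE, with an illustrative 3 affected completers | 3/10 = 30.0% (6.7 to 65.2) | 4/11 = 36.4% (10.9 to 69.2) |

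For 0/10 the upper limit is 1 − 0.025^(1/10) = 30.8%. For 1/11 the lower limit is 1 − 0.975^(1/11) = 0.2%, and the upper limit is the 97.5% point of a Beta(2, 10) distribution, 41.3%. The intervals overlap widely. The material change is whether the event appears in the table.

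**The case against.** The strongest reply is that 13.3 says who will be included and never says *only*. Section 13.4 speaks of the collected data in general. Section 13.5 enters every subject's CRF first and then asks whether anyone should be left out, which suggests inclusion as the default. The outcome is any TEAE. A sponsor could follow all of this and still tabulate the withdrawn subjects.

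That reply stands in part. A reader might infer that the plan expressly bars withdrawn subjects from the safety tables; it does not. But 13.3 is the section on analysis sets, it names one set, and nothing elsewhere requires another. If inclusion is left to a meeting without criteria, held after the data are in, the safety denominator is not prespecified.

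Three further inferences are tempting and are not supported:

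- **That safety data are lost.** They are not. Adverse events, withdrawal reasons and volumes all reach the CRF, and serious events go to the sponsor within 24 hours (12.5). The gap is in the tables.
- **That the standby pool limits omissions to 5 of 15 dosed.** More than five dosed subjects could stop, leaving fewer than ten completers. The standby sentence also covers only the mandatory list, and adverse-event stops are replaced under the last paragraph, which sets no limit.
- **That section 12 removes events during drinking from the definition of an adverse event.** Its sentence about occurrences before the MRE assessment is loose, and the protocol uses that term for both the visit and the scan. But 12.2 starts monitoring at the beginning of intake, and 9.2 treats an event during intake as an adverse event.

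It is also fair that this is a small, uncontrolled, descriptive trial and that the matter concerns a secondary outcome. That limits the consequence but does not justify leaving the denominator open.

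**Conclusion.** The point holds and should be fixed. The only stated population is subjects who finished, and finishing depends on not having an adverse event that stops intake. On its natural reading, the TEAE/TEADR summary leaves such events out, which biases the secondary safety and tolerability result in the product's favour. The primary image-quality result is not affected.

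The size cannot be determined from the documents. The 40% and 65% chances of at least one omission rest on assumed stop rates of 5% and 10%, and on subjects stopping independently. The shift from 1/11 to 0/10 assumes exactly one adverse-event stop and no completer with the same event. The finding that the safety population is undefined needs none of these assumptions.

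**What to change.** - **13.3 and synopsis:** define a safety set of every subject who took any amount of Lumentin 44, including those withdrawn and replaced. Base all TEAE and TEADR tables on it. Keep the completer or evaluable set for image quality and bowel filling.
- **13.4:** report the number dosed, the volume drunk, the number reaching 1.1 L and the reason for stopping, with adverse-event stops and volume failures counted separately.
- **13.5:** state that the clean file meeting cannot remove a dosed subject from the safety set.
- **Optional, section 12:** reword the sentence on occurrences before the MRE assessment so that adverse events clearly count from the start of intake, as in 12.2.

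The cost is a few sentences and a few table rows. Container weights, withdrawal reasons, the Early Termination page and adverse events are already planned for the CRF, so no new visit, sample or subject is needed.

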13.4 Description of Statistical Analyses

A collected data will be summarised using descriptive statistics and confidence intervals. No statistical tests are planned to be conducted.

